#### 1.4 Oxazolidinones

The following adverse reactions were noted in more than 1% of adult subjects in a study of different drug in the oxazolidinone class, linezolid (marketed as Zyvox®): headache, diarrhea, nausea, vomiting, dizziness, rash, anemia, taste alteration, vaginal and oral moniliasis, abnormal liver functions tests, fungal infection, tongue discoloration, and abdominal pain.

The Zyvox® label carries warnings and precautions for myelosuppression, peripheral and optic neuropathy, serotonin syndrome, *Clostridium difficile* associated diarrhea, elevated blood pressure in patients with hypertension, lactic acidosis, convulsions, hypoglycemia, and development of drug-resistant bacteria.

## 1.5 TBI-223 SAD Study Data

### **TBI-223 Single ascending dose (SAD) study (TBI-223-CL-001)**

TBI-223 has been tested in one Phase 1 single-dose ascending dose (SAD) study with healthy volunteers. Study TBI-223-CL-001 was a SAD study designed to evaluate the safety, tolerability, and pharmacokinetics of TBI-223 in healthy adult subjects using an oral suspension, enteric capsule, and Immediate Release (IR) and Sustained Release (SR) tablet formulations.

Part 1 of TBI-223-CL-001 consisted of Cohorts 1-7. Cohorts 1-7 were administered a single dose of 50 to 2600 mg of TBI-223 using the oral suspension. In order to test the absorption in the gastric duodenum, the same subjects of Cohort 3 returned following the completion of Cohort 3 (300 mg suspension), and received TBI-223 as TBI-223 Oral Suspension in oral enteric capsules (300 mg) in an unblinded fashion. Cohort 5 received a single 1200 mg dose of TBI-223 suspension under fed and fasted conditions over two periods. A total of 60 subjects participated in Part 1 of the study.

Part 2 of TBI-223-CL-001 consisted of Cohorts 8 and 9. Cohort 8 consisted of 4 arms, with 6 subjects per arm: In Arms 1-3 of Cohort 8, the 3 SR formulations were administered under fed conditions at 1800 mg, and in Arm 4 the IR tablet was administered under fasting conditions at 2000 mg. In Cohort 9, 6 subjects from Cohort 8, Arm 4, returned to receive the same 2000 mg of the IR tablet under fed conditions. A total of 20 subjects participated in Part 2.

### **Safety Overview:**

#### Part 1

There were no serious AEs (SAEs) or treatment-emergent adverse event (TEAEs) that led to a subject withdrawal or death.

The most frequently reported TEAE was nausea. There were 5 TEAEs reported by 5 subjects; 2 TEAEs were reported by 2 (33.3%) subjects who received TBI-223, 2000 mg and 3 TEAEs were reported by 3 (37.5%) subjects who received TBI-223 2600 mg.

The second most frequently reported TEAE was dizziness. There were 4 TEAEs reported by 4 subjects; 1 TEAE was report by 1 (14.3%) subject who received TBI-223, 1200 mg (fed), 1 TEAE was reported by 1 (16.7%) subject who received TBI-223, 2000 mg, and 2 TEAEs were reported by 2 (25.0%) subjects who received TBI-223, 2600 mg.

There were no changes in neurological examinations from baseline to 72 hours.

The majority of TEAEs were judged by the Investigator as Grade 1 (mild) in severity. Four subjects experienced Grade 2 (moderate) TEAEs (vomiting, urticaria, hypersensitivity, and blood bilirubin increased).

Overall, 4 (6.5%) subjects reported TEAEs that were judged by the Investigator as probably related to the study treatment, 4 (6.5%) subjects reported TEAEs that were judged as possible, 2 (3.2%) subjects reported TEAEs that were judged as unlikely related, and 5 (8.1%) subjects reported TEAEs that were judged as not related to the study treatment.

All TEAEs reported during Part 1 are shown in the table below.

**Table 1 Adverse Events, TEAEs by Primary System Organ Class and Preferred Term, Part 1**

MedDRA Primary System Organ Class Preferred Term	Statistic	Placebo (N=14)	TBI-223 50 mg (N=6)	TBI-223 100 mg (N=6)	TBI-223 300 mg (N=6)	TBI-223 300 mg Capsule (N=6)	TBI-223 600 mg (N=6)	TBI-223 1200 mg (Fasted) (N=8)	TBI-223 1200 mg (Fed) (N=7)	TBI-223 2000 mg (N=6)	TBI-223 2000 mg (N=8)	TBI-223 2600 mg (N=8)	Overall (N=62)
Any TEAE	N (%), No. of Events	4 (28.6), 5	1 (16.7), 1	2 (33.3), 3	1 (16.7), 1	0	0	0	1 (14.3), 1	3 (50.0), 4	3 (37.5), 9	15 (24.2), 24	
Gastrointestinal disorders	N (%), No. of Events	0	0	0	0	0	0	0	0	2 (33.3), 2	3 (37.5), 5	5 (8.1), 7	
Nausea	N (%), No. of Events	0	0	0	0	0	0	0	0	2 (33.3), 2	3 (37.5), 3	5 (8.1), 5	
Vomiting	N (%), No. of Events	0	0	0	0	0	0	0	0	0	2 (25.0), 2	2 (3.2), 2	
Nervous system disorders	N (%), No. of Events	0	0	0	0	0	0	0	1 (14.3), 1	1 (16.7), 1	2 (25.0), 3	4 (6.5), 5	
Dizziness	N (%), No. of Events	0	0	0	0	0	0	0	1 (14.3), 1	1 (16.7), 1	2 (25.0), 2	4 (6.5), 4	
Headache	N (%), No. of Events	0	0	0	0	0	0	0	0	0	1 (12.5), 1	1 (1.6), 1	
Cardiac disorders	N (%), No. of Events	0	0	1 (16.7), 1	0	0	0	0	0	0	1 (12.5), 1	2 (3.2), 2	
Tachycardia	N (%), No. of Events	0	0	1 (16.7), 1	0	0	0	0	0	0	1 (12.5), 1	2 (3.2), 2	

MedDRA Primary System Organ Class Preferred Term	Statistic	Placebo (N=14)	TBI-223 50 mg (N=6)	TBI-223 100 mg (N=6)	TBI-223 300 mg (N=6)	TBI-223 300 mg Capsule (N=6)	TBI-223 600 mg (N=6)	TBI-223 1200 mg (Fasted) (N=8)	TBI-223 1200 mg (Fed) (N=7)	TBI-223 2000 mg (N=6)	TBI-223 2000 mg (N=8)	TBI-223 2600 mg (N=8)	Overall (N=62)
General disorders and administration site conditions	N (%), No. of Events	0	0	2 (33.3), 2	0	0	0	0	0	0	0	0	2 (3.2), 2
Energy increased	N (%), No. of Events	0	0	1 (16.7), 1	0	0	0	0	0	0	0	0	1 (1.6), 1
Medical device site reaction	N (%), No. of Events	0	0	1 (16.7), 1	0	0	0	0	0	0	0	0	1 (1.6), 1
Skin and subcutaneous tissue disorders	N (%), No. of Events	1 (7.1), 1	1 (16.7), 1	0	0	0	0	0	0	0	0	0	2 (3.2), 2
Skin discolouration	N (%), No. of Events	1 (7.1), 1	0	0	0	0	0	0	0	0	0	0	1 (1.6), 1
Urticaria	N (%), No. of Events	0	1 (16.7), 1	0	0	0	0	0	0	0	0	0	1 (1.6), 1
Vascular disorders	N (%), No. of Events	1 (7.1), 2	0	0	0	0	0	0	0	0	0	0	1 (1.6), 2
Hypotension	N (%), No. of Events	1 (7.1), 2	0	0	0	0	0	0	0	0	0	0	1 (1.6), 2
Blood and lymphatic system disorders	N (%), No. of Events	1 (7.1), 1	0	0	0	0	0	0	0	0	0	0	1 (1.6), 1
Neutropenia	N (%), No. of Events	1 (7.1), 1	0	0	0	0	0	0	0	0	0	0	1 (1.6), 1
Immune system disorders	N (%), No. of Events	1 (7.1), 1	0	0	0	0	0	0	0	0	0	0	1 (1.6), 1
Hypersensitivity	N (%), No. of Events	1 (7.1), 1	0	0	0	0	0	0	0	0	0	0	1 (1.6), 1
Investigations	N (%), No. of Events	0	0	0	1 (16.7), 1	0	0	0	0	0	0	0	1 (1.6), 1
Blood bilirubin increased	N (%), No. of Events	0	0	0	1 (16.7), 1	0	0	0	0	0	0	0	1 (1.6), 1
Musculoskeletal and connective tissue disorders	N (%), No. of Events	0	0	0	0	0	0	0	0	1 (16.7), 1	0	1 (1.6), 1	

MedDRA Primary System Organ Class Preferred Term	Statistic	Placebo (N=14)	TBI-223 50 mg (N=6)	TBI-223 100 mg (N=6)	TBI-223 300 mg (N=6)	TBI-223 300 mg Capsule (N=6)	TBI-223 600 mg (N=6)	TBI-223 1200 mg (Fasted) (N=8)	TBI-223 1200 mg (Fed) (N=7)	TBI-223 2000 mg (N=6)	TBI-223 2000 mg (N=6)	TBI-223 2600 mg (N=8)	Overall (N=62)
Back pain	N (%), No. of Events	0	0	0	0	0	0	0	0	1 (16.7), 1	0	1 (1.6), 1	

MedDRA = Medical Dictionary for Regulatory Activities, Version 23.0

### **Cardiac Assessments (ECG and Holter)**

#### Electrocardiograms

There were no clinically significant findings for ECGs.

#### Heart Rhythm and Cardiac Conduction

In Part 1 of the study, the effect of TBI-223 oral suspension on ECG parameters was evaluated using continuous 12-lead ECG (Holter) monitoring. Serial ECGs were extracted from the Holter recordings at prespecified time points starting on Day -1 through 48 hours post-dose. At baseline, data were available from 6 subjects in each of the 50, 100, 300, 600 and 2000 mg TBI-223 group, 8 subjects in the 1200 and 2600 mg group and from 14 placebo subjects pooled from all cohorts.

TBI-223 Oral Suspension at the studied doses did not have a clinically relevant effect on HR. The pattern across dose groups and relation to the observed PK profile of TBI-223 and M2 do not suggest that the drug or metabolite exert a clinically relevant effect on HR.

In the by-time point analysis for QTcF, mean placebo-corrected  $\Delta\Delta\text{QTcF}$  ( $\Delta\Delta\text{QTcF}$ ) ranged from -8.9 ms at 12 hours post-dose in the 600 mg group to 13.3 ms at 5 hours post-dose in the 2000 mg dose group. In the 2 highest dose groups (2000 mg and 2600 mg), mean  $\Delta\Delta\text{QTcF}$  was 13.1 ms and 13.3 ms at 4 and 5 hours and 12.4 ms at 1 hour post-dose, respectively.

In the concentration-QTc analysis, a full model including TBI-223 and its metabolite M2 was selected as the primary model. The estimated population slope of the concentration-QTc relationship was 0.0004 ms per  $\mu\text{g}/\text{L}$  (90% CI: -0.00005 to 0.00093) for TBI-223, 0.001 ms per  $\mu\text{g}/\text{L}$  (90% CI: -0.0010 to 0.0034) for M2 with a treatment effect-specific intercept of 1.6 ms (90% CI: -1.01 to 4.16). The predicted effect on  $\Delta\Delta\text{QTcF}$  at the geometric mean  $C_{\text{max}}$  of TBI-223 and of M2 after a single dose of 1200 mg, also accounting for the effect of M2 and TBI-223 at the same time points ( $T_{\text{max}}$  of TBI-223 and M2, respectively), was 7.47 and 7.16 ms, with an upper bound of the 90% CI of 10.06 and 10.20 ms, respectively. In the concentration-QTc analysis with TBI-223 alone and M2 alone, an effect on  $\Delta\Delta\text{QTcF}$  can be excluded at TBI-223 and M2 concentrations up to  $\sim 8140 \mu\text{g}/\text{L}$  and  $\sim 2040 \mu\text{g}/\text{L}$ , respectively.

TBI-223 Oral Suspension at the studied doses did not have a clinically relevant effect on cardiac conduction, i.e., the PR and QRS intervals.

### **Cardiovascular Summary**

In summary, TBI-223 oral suspension at the studied doses had no clinically relevant effects on HR or on cardiac conduction (the PR and QRS intervals). Based on the concentration-QTc analysis, a QTcF effect ( $\Delta\Delta\text{QTcF}$ ) exceeding 10 ms can be excluded for plasma concentrations of TBI-223 and M2 up to  $\sim 8000 \mu\text{g/L}$  and  $\sim 2000 \mu\text{g/L}$ , respectively.

### **Part 2**

There were no SAEs or TEAEs that led to a subject withdrawal or death.

The most frequently reported TEAE was vessel puncture site inflammation. There were 3 TEAEs reported by 3 subjects; 2 TEAEs were reported by 2 (33.3%) subjects who received TBI-223, 1800 mg SR Tablet (Prototype 2, fed), and 1 TEAE was reported by 1 (16.7%) subject who received TBI-223, 2000 mg IR Tablet (fasted).

The second most frequently reported TEAE was dizziness. There were 3 TEAEs reported by 2 subjects; 2 TEAEs were reported by 2 (33.3%) subjects who received TBI-223, 2000 mg IR Tablet (fasted) and 1 TEAE was reported by 1 (16.7%) subject who received TBI-223, 2000 mg IR Tablet (fed).

All TEAEs reported during Part 2 were Grade 1 (mild) in severity.

Overall, 1 (4.2%) subject reported a TEAE that was judged by the Investigator as probably related to the study treatment, 3 (12.5%) subjects reported TEAEs that were judged as possible, and 4 (16.7%) subjects reported TEAEs that were judged as not related to the study treatment.

There were no TEAEs related to clinically significant out-of-range vital sign measurements or laboratory values.

No clinically significant abnormalities in ECGs were observed.

There were no changes in neurological examinations from baseline to 48 hours.

All TEAEs reported during Part 2 are shown in the table below.

**Table 2 Adverse Events, TEAEs by Primary System Organ Class and Preferred Term, Part 2**

MedDRA Primary System Organ Class Preferred Term	Statistic	TBI-223 1800 mg SR-1 tablet (Fed) (N=6)	TBI-223 1800 mg SR-2 tablet (Fed) (N=6)	TBI-223 1800 mg SR-3 tablet (Fed) (N=6)	TBI-223 2000 mg IR tablet (Fasted) (N=6)	TBI-223 2000 mg IR tablet (Fed) (N=6)	Overall (N=24)
Any TEAE	N (%), No. of Events	1 (16.7), 1	2 (33.3), 2	2 (33.3), 3	3 (50.0), 6	2 (33.3), 2	8 (33.3), 14
General disorders and administration site conditions	N (%), No. of Events	0	2 (33.3), 2	2 (33.3), 3	1 (16.7), 2	0	5 (20.8), 7
Vessel puncture site inflammation	N (%), No. of Events	0	2 (33.3), 2	0	1 (16.7), 1	0	3 (12.5), 3
Chest discomfort	N (%), No. of Events	0	0	0	1 (16.7), 1	0	1 (4.2), 1
Vessel puncture site pain	N (%), No. of Events	0	0	1 (16.7), 1	0	0	1 (4.2), 1
Vessel puncture site reaction	N (%), No. of Events	0	0	1 (16.7), 1	0	0	1 (4.2), 1
Vessel puncture site swelling	N (%), No. of Events	0	0	1 (16.7), 1	0	0	1 (4.2), 1
Nervous system disorders	N (%), No. of Events	1 (16.7), 1	0	0	3 (50.0), 3	1 (16.7), 1	4 (16.7), 5
Dizziness	N (%), No. of Events	0	0	0	2 (33.3), 2	1 (16.7), 1	2 (8.3), 3
Disturbance in attention	N (%), No. of Events	0	0	0	1 (16.7), 1	0	1 (4.2), 1
Headache	N (%), No. of Events	1 (16.7), 1	0	0	0	0	1 (4.2), 1
Gastrointestinal disorders	N (%), No. of Events	0	0	0	1 (16.7), 1	1 (16.7), 1	1 (4.2), 2
Abdominal pain	N (%), No. of Events	0	0	0	0	1 (16.7), 1	1 (4.2), 1
Nausea	N (%), No. of Events	0	0	0	1 (16.7), 1	0	1 (4.2), 1

MedDRA = Medical Dictionary for Regulatory Activities, Version 23.0.

**Safety Summary:****Part 1**

In part 1 of the study all subjects were dosed with TBI-223 oral suspension.

Overall, TBI-223 was well-tolerated when administered as an oral suspension and oral enteric capsules in healthy subjects under fed and fasted conditions at doses from 50 mg to 2600 mg. At 2600 mg of the oral suspension, the arithmetic mean  $C_{max}$  of TBI-223 was 16.2  $\mu$ g/mL. Two of six subjects had  $C_{max}$  exceeding 20  $\mu$ g/mL (21.0 and 22.0  $\mu$ g/mL). The arithmetic mean  $AUC_{0-inf}$  of TBI-223 was 127  $\mu$ g.h/mL, with the maximum value being 190  $\mu$ g.h/mL.

## Part 2

In Part 2 of the study all subjects were dosed with TBI-223 Immediate (IR) and Sustained (SR) release formulations.

Overall, the TBI-223 was well-tolerated when administered as a tablet formulation in healthy subjects under fed and fasted conditions at doses of 2000 mg (IR) and 1800 mg (SR). The highest concentrations of TBI-223 were seen with 2000 mg IR under fed conditions, where the arithmetic mean  $C_{max}$  was 19.7  $\mu$ g/mL and where two of six subjects had  $C_{max}$  exceeding 20  $\mu$ g/mL (25.9 and 27.5  $\mu$ g/mL). That group also experienced the highest arithmetic mean  $AUC_{0-inf}$  of TBI-223, 100  $\mu$ g.h/mL, with the maximum value being 150  $\mu$ g.h/mL.

## **Pharmacokinetic Summary (Suspension):**

### Single Ascending TBI-223 Doses, Cohorts 1-7, Fasted (Part 1)

After administrations of single TBI-223 oral suspension doses under fasted conditions, median TBI-223  $T_{max}$  ranged from 1.00 h (Cohort 1, 50 mg) to 2.25 h (Cohort 7, 2600 mg). TBI-223 exposure ( $C_{max}$  and AUCs) increased in a nearly dose-proportional manner with an increase in dose under fasted conditions dose over the 50 mg to 2600 mg dose range. Slope ( $\beta_1$ ) were close to 1 for each parameter and the 90% confidence intervals nearly included 1. Slope estimates and 90% confidence intervals (90% CI) were 0.9310 (0.8622 - 0.9997) for  $C_{max}$ , 1.1385 (1.0906 – 1.1863) for  $AUC_{0-t}$ , and 1.1338 (1.0853 – 1.1823) for  $AUC_{0-inf}$ .

### Formulation Effect, Cohort 3, 300 mg, Capsule vs. Oral Suspension (Part 1)

Median TBI-223  $T_{max}$  was observed at approximately 3.6 h later for the TBI-223 capsule formulation (5.00 h) compared to that after the oral suspension (1.37 h). Maximum TBI-223 exposure ( $C_{max}$ ) was approximately 58% lower after administration of the capsule formulation compared to that after the oral suspension formulation; total TBI-223 exposure (AUCs) was similar for capsule and oral suspension formulations. This outcome demonstrated uptake in the duodenum and therefore supported evaluating a sustained release formulation which could result in more T>MIC Geometric mean ratios and 90% CIs for  $C_{max}$ ,  $AUC_{0-t}$ , and  $AUC_{0-inf}$  were 42.46% (31.57% - 57.10%), 94.43% (90.28% - 98.76%), and 94.73% (90.58% - 99.06%), respectively.

Food Effect, Cohort 5, TBI-223 Oral suspension 1200 mg; (Part 1)

Median  $T_{max}$  was 1.50 h after drug administration under fed and fasted conditions. Maximum and total TBI-223 exposure ( $C_{max}$  and AUCs) were similar for fed and fasted conditions. Geometric mean ratios and 90% CIs for  $C_{max}$ ,  $AUC_{0-t}$ , and  $AUC_{0-inf}$  were 103.34% (87.00% - 122.75%), 103.23% (97.80% - 108.96%), and 102.79% (96.37% - 109.64%), respectively.

Food Effect, TBI-223 IR Tablets, 2000 mg; (Part 2)

Administration of IR tablets with food delayed TBI-223  $T_{max}$  by approximately 1 h. Administration of TBI-223 IR tablets (2000 mg) with food increased TBI-223  $C_{max}$  by approximately 51%. TBI-223 AUCs were slightly higher (~16%) under fed conditions compared to that under fasted conditions. Geometric mean ratios and 90% CIs for  $C_{max}$ ,  $AUC_{0-t}$ , and  $AUC_{0-inf}$  were 151.24% (127.91% - 178.82%), 115.73% (112.08% - 119.50%), and 115.70% (112.06% - 119.47%), respectively.

**Different Formulation (Tablets - Immediate and Sustained release)**

**Pharmacokinetics:**

Sustained-release (SR) Tablet Prototypes 1, 2, and 3 (Fed), 1800 mg vs. IR Tablets 2000 mg (Fasted), (Part 2)

Median TBI-223  $T_{max}$  was observed approximately 4.5 to 5.5 h later for the SR prototypes administered with food compared to the IR formulation under fasted conditions.

Maximum TBI-223 exposure (normalized  $C_{max}$ ) was approximately 46%, 28%, and 34% lower after administrations of SR-1, SR-2, and SR-3 under fed conditions, compared to IR tablet under fasted conditions. Total TBI-223 exposure (normalized  $AUC_{0-t}$  and  $AUC_{0-inf}$ ) was approximately 19% lower for SR-1 and SR-2 administered under fed conditions compared to IR tablets administered under fasted conditions; AUCs were similar for SR-3 and IR.

Geometric mean ratios and 90% CIs for SR-1 normalized  $C_{max}$ ,  $AUC_{0-t}$ , and  $AUC_{0-inf}$  were 53.53% (40.10% - 71.45%), 81.11% (62.92% - 104.56%), and 81.52% (63.26% - 105.04%), respectively. Geometric mean ratios and 90% CIs for SR-2 normalized  $C_{max}$ ,  $AUC_{0-t}$ , and  $AUC_{0-inf}$  were 71.70% (53.71% - 95.71%), 80.55% (62.49% - 103.84%), and 80.56% (62.51% - 103.81%), respectively. Geometric mean ratios and 90% CIs for SR-3 normalized  $C_{max}$ ,  $AUC_{0-t}$ , and  $AUC_{0-inf}$  were 66.31% (49.67% - 88.53%), 95.71% (74.25% - 123.38%), and 95.73% (74.29% - 123.35%), respectively.

Sustained-release (SR) Tablet Prototypes 1, 2, and 3 (Fed), 1800 mg vs. IR Tablets 2000 mg (Fed), (Part 2)

Median TBI-223  $T_{max}$  was observed approximately 3.5 to 4.5 h later for the SR prototypes compared to the IR formulation under fed conditions.

Maximum TBI-223 exposure (normalized  $C_{max}$ ) was approximately 65%, 53%, and 56% lower after administrations of SR-1, SR-2, and SR-3 compared to IR tablet under fed conditions. Total TBI-223 exposure (normalized  $AUC_{0-t}$  and  $AUC_{0-inf}$ ) was approximately 17%-30% lower after administrations of SR-1, SR-2, and SR-3 compared to IR tablet under fed conditions.

Geometric mean ratios and 90% CIs for SR-1 normalized  $C_{max}$ ,  $AUC_{0-t}$ , and  $AUC_{0-inf}$  were 35.39% (26.04% - 48.10%), 70.09% (54.10% - 90.81%), and 70.45% (54.40% - 91.24%), respectively. Geometric mean ratios and 90% CIs for SR-2 normalized  $C_{max}$ ,  $AUC_{0-t}$ , and  $AUC_{0-inf}$  were 47.41% (34.88% - 64.43%), 69.60% (53.72% - 90.18%), and 69.62% (53.76% - 90.17%), respectively. Geometric mean ratios and 90% CIs for SR-3 normalized  $C_{max}$ ,  $AUC_{0-t}$ , and  $AUC_{0-inf}$  were 43.85% (32.26% - 59.59%), 82.70% (63.83% - 107.15%), and 82.74% (63.88% - 107.15%), respectively.

## **1.6 Adverse Effects, Warnings, and Precautions**

Given the key safety findings in the SAD (TBI-223) study, TBI-223-CL-001 and nonclinical safety studies for the cardiovascular system (prolonged QTc) and the nervous (CNS) system (tremors), we will implement the following monitoring procedures.

### **Cardiovascular Monitoring**

Cardiovascular monitoring will be conducted and include the following at both protocol-defined time points and whenever deemed necessary by the study investigator. Subjects treated with TBI-223 will have their ECGs evaluated prior to treatment and during treatment. During treatment, the timing of ECGs will be guided by pharmacokinetic (PK) data so that collection occurs around the estimated  $T_{max}$ .

ECGs will be interpreted and signed and dated by the Principal Investigator or designee. The ECGs will be classified as normal, having a clinically insignificant abnormality, or having a clinically significant abnormality. All clinically significant abnormalities will be recorded as AEs. In addition, ECG parameters of ventricular rate, PQ or PR interval, QRS duration, and QT interval (corrected and uncorrected) will be noted on the case report form (CRF). If a patient's corrected QT interval (QTcF) exceeds 500 msec while on treatment or there is a change from baseline exceeding 60 msec, TBI-223 administration should be stopped, and the patient monitored with ECGs and/or telemetry until the QTcF returns to pre-treatment levels.

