### **3.2 Cohort Stopping Rules for Subjects Receiving Active Drug:**

If any of the cohort stopping rules are met, cohort dosing must be stopped until review of the data by the Sponsor and the Investigator.

Rules for stopping dosing of a cohort include the following:

1. One subject experiences a drug-related SAE.
2. Two or more subjects develop Grade 3 or higher central nervous system AE considered related to drug.
3. Two or more ( $\geq 2$ ) subjects develop QTcF  $> 500$  msec with an increase from baseline  $> 60$  msec after completion of repeat testing.
4. Two or more subjects experience confirmed Grade 3 or Grade 4 cardiac rhythm disturbances considered related to drug.

If any of the cohort stopping rules are met, cohort dosing must be stopped until the data has been reviewed by the Sponsor, Investigator and Dose Escalating meeting (DEM) before dosing is resumed, or other actions taken, or the decision made to discontinue the cohort. Refer to Section [6.2.5](#) for unblinding procedures. The IRB or Ethics committee (EC) should be immediately notified according to their regulations.

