13. QTcF interval >450 msec for males or >470 msec for females at screening, Day -1, or Day 1 (predose), or history of prolonged QT syndrome. For the triplicate ECGs taken at screening and on Day -1, the average QTcF interval of the three ECG recordings will be used to determine qualification.
14. Family history of long-QT syndrome or sudden death without a preceding diagnosis of a condition that could be causative of sudden death (such as known coronary artery disease, congestive heart failure, or terminal cancer).
15. History of any of the following:
  - Serotonin syndrome
  - Seizures or seizure disorders, other than childhood febrile seizures
  - Brain surgery
  - History of head injury in the last 5 years
  - Any serious disorder of the nervous system particularly one that may lower the seizure threshold.
16. Lactose intolerant.

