#### 6.9.6 12-Lead Electrocardiograms

Safety 12-lead ECGs will be recorded and printed for on-site review by the Principal Investigator or designee at the times noted on the events schedule ([Table 6](#) for food-effect cohorts and [Table 7](#) for non-food-effect cohort).

The predose ECG should be completed within 20 minutes prior to the predose blood draw.

All safety ECGs will be performed after the subject has been in supine position for a minimum of 5 minutes.

If a subject experiences a post-dosing QTcF  $>500$  msec or a change-from-baseline QTcF  $\geq 60$  msec, after repeat testing, additional ECGs should be recorded until normalization or return to baseline.

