### **8.4 Indications for Subject Withdrawal**

Subjects will be free to withdraw at any time for any reason, or they may be withdrawn if necessary, to protect their health and safety or the integrity of the study data.

The final report will include reasons for withdrawals. In the event of an early termination, subjects will undergo the procedures described in Section 6.8.

Subjects who experience emesis may be replaced if the emesis could potentially impact drug absorption and therefore the pharmacokinetic data. Cases of emesis will be evaluated by the Sponsor and Principal Investigator to determine if subject replacement is needed.

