- k. 12-lead safety ECGs will be printed and reviewed on-site by the Principal Investigator or designee. Triplicate ECGs will be completed at screening, Day -2, Day -1, and on Day 26 or upon early withdrawal. All other time points will be single ECG readings. ECGs may be done within 2 hours prior

Protocol TBI-223 CL-002 Version 1.0

to time of dosing and at 3, 6, 12 and 16 hours postdose on Days 1, 4, 8, 10, 12, 14, 17, and on Days 18 and 20. Another single ECG reading will be performed on the morning of Day 20 before discharge. The predose ECG should be completed within 20 minutes prior to the predose blood draw. If a subject experiences a post-dosing QTcF >500 msec with a change-from-baseline QTcF >60 msec, after repeat testing, additional ECGs should be recorded until normalization or return to baseline

- l. Predose trough blood samples will be drawn on Day 1 and daily starting on Day 4.
- m. Duplicate plasma samples will be generated from all blood pharmacokinetic samples.
- n. Postdose blood plasma samples will be drawn at the following timepoints:
  - Day 1: 0.5, 1, 2, 3, 4, 5, 6, 7, 8, 12, 16, 20, 24, 30, 36, 42, 48, 54, 60, and 72 hours. The 72-hour sample is the predose sample of Day 4.
  - Day 4: 0.5, 1, 2, 3, 4, 5, 6, 7, 8, 12, 16, 20, and 24 hours. The 24-hour sample is the predose sample of Day 5.
  - Day 17: 0.5, 1, 2, 3, 4, 5, 6, 7, 8, 12, 16, 20, 24, 30, 36, 42, 48, 54, 60, and 72 hours

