- k. 12-lead safety ECGs will be printed and reviewed on-site by the Principal Investigator or designee. Triplicate ECGs will be completed at screening, Day -2, Day -1, and on Day 23 or upon early withdrawal. All other time points will be single ECG readings. ECGs may be done within 2 hours prior to time of dosing and at 3, 6, 12, and 16 hours postdose on Days 1, 2, 3, 8, 12. Another single ECG reading will be performed on the morning of Day 17 before discharge. The predose ECG should be completed within 20 minutes prior to the pre-dose blood draw. If a subject experiences a post-dosing QTcF  $>500$  msec with a change-from-baseline QTcF  $>60$  msec, after repeat testing, additional ECGs should be recorded until normalization or return to baseline
- l. Predose trough blood samples will be drawn daily starting on Day 1.
- m. Duplicate plasma samples will be generated from all blood pharmacokinetic samples.
- n. Postdose blood plasma samples will be drawn at the following timepoints:
  - Day 1: 0.5, 1, 2, 3, 4, 5, 6, 7, 8, 12, 16, 20, and 24 hours. The 24-hour sample is the predose sample of Day 2.
  - Day 14-17: 0.5, 1, 2, 3, 4, 5, 6, 7, 8, 12, 16, 20, 24, 30, 36, 42, 48, 54, 60, and 72 hours

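### Section 6.9.6 and schedule note k set different QTcF triggers for the same follow-up ECGs, and neither carries the single-subject drug stop that Section 1.6 requires

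*Protocol*

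**What the plan says.** Four places in the protocol attach an action to an on-treatment QTcF reading.

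- **Section 1.6, Cardiovascular Monitoring.** If QTcF "exceeds 500 msec while on treatment or there is a change from baseline exceeding 60 msec, TBI-223 administration should be stopped". Either limit is enough. No repeat test is mentioned. The subject is then followed with ECGs, telemetry or both until QTcF is back at its pre-treatment level.
- **Section 6.9.6, 12-Lead Electrocardiograms.** The trigger is QTcF above 500 msec or a rise of 60 msec or more. The instruction is: "after repeat testing, additional ECGs should be recorded until normalization or return to baseline". Nothing is said about the dose.
- **Note k of Table 12 (Cohorts 1 and 2).** The trigger is "post-dosing QTcF >500 msec with a change-from-baseline QTcF >60 msec, after repeat testing, additional ECGs should be recorded". Both limits are needed. Note k of Table 13 (Cohort 3) joins the limits in the same way: "msec with a change-from-baseline QTcF". Neither note mentions the dose.
- **Section 3.2, cohort stopping rule 3.** It counts subjects above 500 "msec with an increase from baseline" above 60 msec after repeat testing, and needs two or more of them. This rule is for the cohort, not the subject.

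Section 8.4 sets no QTcF limit. It says only that "they may be withdrawn if necessary, to protect their health and safety or the integrity of the study data".

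**The concern.** Section 6.9.6 and note k prescribe the same action for the same event, but one joins the limits with *or* and the other with *with*. Graded severity cannot explain two triggers for one action. The order is also inverted across the protocol: the mildest response, extra ECGs under note k, needs both limits, while the strongest response for a subject, stopping drug under Section 1.6, needs only one.

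Section 1.6 names QTc prolongation as one of the two safety findings that drive monitoring. Section 1.5 reports that a QTcF effect "exceeding 10 ms can be excluded for plasma concentrations of TBI-223 and M2 up to" about 8000 µg/L and 2000 µg/L respectively. Table 3 predicts a Cmax of 9.7 µg/mL in Cohort 3, which is 9.7 × 1000 = 9700 µg/L and so above the TBI-223 level. Dosing is daily during the 14-day course. Someone working only from the ECG section or the schedule is not told there to withhold the next morning's dose.

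**Working it through.** The plan gives no figure to reproduce. The check is to write the rules side by side and apply them to the same readings.

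Let b be the subject's baseline QTcF and x an on-treatment reading, both in msec. For Section 6.9.6 and note k, x is the reading after repeat testing.

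- Section 1.6, stop drug: x > 500 **or** x − b > 60.
- Section 6.9.6, more ECGs: x > 500 **or** x − b ≥ 60.
- Note k, more ECGs: x > 500 **and** x − b > 60.

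**Where Section 6.9.6 and note k disagree.** Section 6.9.6 acts once x passes the lower of 500 and b + 60. Note k acts only once x passes the higher of the two. They disagree in between, over a width of |500 − (b + 60)| = |440 − b|.

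| Baseline b | b + 60 | 6.9.6 asks for ECGs, note k does not | Width |
|---|---|---|---|
| 400 | 460 | 460 to 500 | 40 |
| 420 | 480 | 480 to 500 | 20 |
| 440 | 500 | exactly 500 only | 0 |
| 450 | 510 | above 500 to 510 | 10 |
| 470 | 530 | above 500 to 530 | 30 |

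All these baselines are eligible, the last for women only. Exclusion 13 bars a "QTcF interval >450 msec for males or >470 msec for females at screening, Day -1, or Day 1 (predose").

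**Where Section 1.6 stops drug and note k is silent.** This is the same band without its lower end point when b is 440 or less, because Section 1.6 uses >60 and Section 6.9.6 uses ≥60. At b = 440 nothing is left of it.

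**Example readings** (illustrative values, each confirmed on repeat):

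| b | x | Change | Section 1.6 | Section 6.9.6 | Note k | Counts for rule 3 of 3.2 |
|---|---|---|---|---|---|---|
| 400 | 465 | +65 | stop drug | more ECGs | nothing | no |
| 450 | 505 | +55 | stop drug | more ECGs | nothing | no |
| 400 | 460 | +60 | no stop | more ECGs | nothing | no |
| 430 | 505 | +75 | stop drug | more ECGs | more ECGs | yes, one of two |

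The first two rows give three different instructions for one reading. In the last row all three rules fire, but only Section 1.6 mentions the dose.

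**Repeat testing.** Take b = 400, a first reading of 465 and a repeat of 450. The first change is +65 and the repeat change is +50. Read literally, Section 1.6 stops drug on the first reading, while Section 6.9.6 and note k ask for nothing. The text does not say whether the repeat-test condition is meant to apply to the stop as well.

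**The case against.** The strongest reply is that nothing essential is missing. Section 1.6 sits in the introduction but is worded as procedures that will be carried out, so it is operative. The ECGs are read by the investigator or a designee, who is bound by the whole protocol and may also withdraw a subject for safety under Section 8.4. Neither Section 6.9.6 nor note k says that dosing continues, so an investigator who stops drug under Section 1.6 breaches nothing. Section 1.6 itself requires ECG or telemetry follow-up after a stop, which covers most of what note k leaves out. The gap between >60 and ≥60 msec has little practical weight.

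All of that stands, and it limits the point to consistency and placement. It does not settle two things: which trigger governs the extra ECGs, and whether a repeat must precede the stop. Full compliance with every section answers neither.

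A reader might infer three stronger points that the documents do not support:

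- *That the protocol has no individual QTcF stop, or that subjects would be dosed beyond it.* Section 1.6 has the stop.
- *That cohort rule 3 is wrong because it needs both limits.* A stricter rule for pausing a whole cohort can be deliberate.
- *That an unrepeated stop is an error because it would end dosing too often.* The protocol gives no standard deviation for change in QTcF, so no such rate can be derived from it. Stopping on one reading is a defensible cautious rule in healthy volunteers given a drug with a QT signal.

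**Conclusion.** The point holds as an inconsistency that should be corrected. Section 6.9.6 and note k contradict each other on when additional ECGs are required, over a band |440 − b| msec wide, and neither repeats the drug stop that binds through Section 1.6. Note k asks for nothing in some subjects whose drug Section 1.6 stops. The band follows from the wording alone and rests on no assumption about variability or drug effect.

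How often a reading would fall in the band cannot be estimated from the protocol, and no frequency is claimed. The predicted Cohort 3 exposure shows why the QTcF rules deserve care. It does not show that a 60 msec rise is likely: the level of about 8000 µg/L concerns an average effect of 10 ms, and the largest mean placebo-corrected effect reported in Section 1.5 is 13.3 ms.

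**What to change.** 1. **Note k, Tables 12 and 13.** Replace the both-limits criterion with the either-limit criterion of Section 6.9.6, or simply refer to Section 6.9.6.
2. **Section 6.9.6.** Keep QTcF above 500 msec or a rise of at least 60 msec as the trigger for additional ECGs, and add: *If QTcF exceeds 500 msec or the change from baseline exceeds 60 msec, TBI-223 is stopped in that subject per Section 1.6; the next dose is not given.*
3. **Repeat testing.** The sponsor and investigator should decide whether a repeat ECG must confirm the reading before the stop, and say so once. Dosing is held until that is settled for the subject. Requiring confirmation has a price, since a true rise may fail to repeat, so this is a medical decision.

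Section 3.2 needs no change for this purpose.

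The cost is one added sentence, two edited footnotes and one decision. No visits are added. Where a repeat is wanted there is time for it: the last scheduled ECG on a dosing day is 16 hours after the dose, which leaves 24 − 16 = 8 hours before the next daily dose. The downside is a few more follow-up ECGs than note k now requires.
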